Objectives	This is a prospective study to provide access to an investigational device and reagents used for progenitor cell sorting of a stem cell transplant donor graft to determine the ability of CD34+ cell selection and T Cell depletion (using the
Objectives	CliniMACS [®] device as the sole GvHD prophylaxis) to prevent severe (grade III-IV) acute GvHD in recipients of mismatched related or unrelated donor hematopoietic stem cell transplants or with borderline organ function who might not endure the often toxic side-effects of traditional post-HSCT immunosuppressive therapy.
Primary Endpoint(s)	The primary endpoint of the study is the incidence of severe (grade III/IV) acute GvHD occurring by Day +100 after transplant.
Secondary Endpoint(s)	Outcomes measures for the secondary endpoints will include: Engraftment: The incidence of primary graft failure and graft rejection will be determined. Chimerism at Day 100: The percentage of donor cells will be reported for all evaluable (without disease progression) patients. Immune recovery: The time to CD4 count >100 and > 200 and PHA≥ 10% and 30% will be calculated. Severe toxicities: The incidence of severe toxicities will be determined. This will include grade 3/4 stem cell product infusion-related toxicity. Post-transplant infections (bacterial, viral and fungal): Post-transplant infections will be described by incidence and type. Post-transplant lymphoproliferative disease (PTLD): The incidence of PTLD will be calculated. Transplant-related mortality (TRM): The incidence of TRM will be calculated at Day 100 after transplant and at one year. Disease-free survival. Overall survival: Overall survival will be estimated using the Kaplan-Meier method. Device (CliniMACS®) performance parameters: The parameters will be summarized for all products that are processed and median and ranges will be determined.
Study Design	Participants will be enrolled with alternative (mismatched/haplocompatible) related/unrelated donors or matched related/unrelated donors for an initial HSCT.
Study Centers	This is a Stanford University, Principle Investigator (PI) initiated protocol conducted at LPCH and Stanford Hospital and Clinics.
Duration of Study per Subject	Individual participants will be followed for outcomes related to the experimental device including acute and chronic GvHD and engraftment for a minimum of one year. Subsequent follow-up care will follow the standard for all transplant patients.

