Subject Population	Pediatric and adult patients up to 35 years old, of any gender, and ethnic background, with malignant and/or non-malignant diagnosis that are treatable though allogeneic stem cell transplantation.

Inclusion Criteria:

- Participants greater than one month of age.
- Participant has a disorder that can be treated with a hematopoietic stem cell transplant
 - Participant's is eligible for an allogenic HSCT as per current institutional SOP and FACT standards
- Participant must have a related or unrelated matched or mismatchedrelated donor who is:
 - Able to receive granulocyte colony-stimulating factor (G-CSF) and undergo apheresis either through placement of catheters in antecubital veins or a temporary central venous catheter OR agrees on a bone marrow harvest;
 - Healthy as per donor selection screening (following current SOP based on standards of foundation for accreditation of cellular therapy and stem cell transplantation – FACT);
 - Willing to participate and sign consent.
- Participant or Legal Authorized Representative is able to sign informed consent (and signed assent, if applicable) for transplant.

Exclusion Criteria:

- Participant does not qualify for an allogeneic transplant due to medical screening, underlying disease, or lack of alternative donors.
- Any condition that compromises compliance with the procedures of this protocol, as judged by the principal investigator.

Principal Investigator will evaluate and report all grade 3 or 4 adverse reactions that are unexpected and possibly related to the investigation in process and are not expected TRM as per protocol definition. If it becomes clear that the study treatment is less effective than other available treatments or the toxicity is unacceptable we will follow the stopping rules.

Stopping rule for primary graft failure: The first 30 enrolled patients (related and unrelated) will be evaluated for the stopping rule for primary graft failure. The trial is stopped if there are ≥ b graft failures out of k resolved patients. Only points where stopping is possible are listed.

Discontinuation Criteria (Safety Considerations)

Eligibility criteria

k	2	4	5	6	8	9	10	12	13	14	15	16	18	19	20	21	23	24	25	26	27	28	30
b	2	3	3	3	4	4	4	5	5	5	5	5	6	6	6	6	7	7	7	7	7	7	8

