CNS	Central nervous system
Co-PI(s)	Co-Investigator(s)
CRF	Case report/record form
CR	Complete response
CTCAE	Common Terminology Criteria for Adverse Events
CTN	Clinical Trials Network
DFS	Disease Free Survival
DLI	Donor Leukocyte Infusion
DLT	Dose Limiting Toxicity
DSMB	Data Safety Monitoring Board
DSMC	Data and Safety Monitoring Committee
EBV	Epstein Barr Virus
EC	Ethics Committee
ECG	Electrocardiogram
Echo/ECCO	Echocardiogram

EFS	Event-free survival
EIDE	Emergency investigational device exemption
EIND	Emergency Investigational new drug
F	Fahrenheit
FA	Fanconi Anemia
FACT	Foundation for the Accreditation of Cellular Therapy
FDA	Food and Drug Administration
GCP	Good clinical practice
G-CSF	Human granulocyte-colony stimulating factor
GI	Gastrointestinal
GFR	Glomerular filtration rate
GvHD	Graft-versus-Host Disease
HBV	Hepatitis B Virus
HCG	Human chorionic gonadotropin
HCV	Hepatitis C Virus
Hgb	Hemoglobin
HIV	Human Immunodeficiency Virus
HHV	Human Herpes Virus
HLA	Human leukocyte antigen
HPF	High-power field
HR	Heart rate
HSCs	Hematopoietic stem cells
HSCT	Hematopoietic Stem Cell Transplant
HSV	Herpes Simplex Virus
HTN	Hypertensions
HUD	Humanitarian Use Device
IB	Investigator Brochure
IDE	Investigational Device Exemption
IND	Investigational New Drug
IRB	Institutional Review Board
IV	Intravenous
LAR	Legal authorized representative
LLN	Lower limit of normal
LN ₂	Liquid Nitrogen
mAb	Monoconal antibody
MDS	Myelodysplastic Syndrome
MRD	Matched related donor
NCI	National Cancer Institute
NCI CTCAE	National Cancer Institute common terminology criteria for adverse events
NHL	Non-Hodgkin's Lymphoma

NIH	National Institutes of Health
NK	Natural killer
NMDP	National Marrow Donor Program
OS	Overall survival
PBSC	Peripheral blood stem cells
PCR	Polymerase chain reaction
PD	Progressive diseased
Peds	Pediatric patients
PFS	Progression free survival
PI	Principal investigator
PLT	Platelet
PMRD	Partially matched donor
PPA	Per protocol analysis
PR	Partial response
PTLD	Post-transplant lymphoproliferative disorder
RR	Response rate
SAE	Serious adverse event
SCCI	Stanford Center for Clinical Informatics
SD	Stable disease
SCT	Stem cell transplant
SCTT	Stanford Blood and Marrow Cellular Therapeutics & Transplantation Laboratory
SOP	Standard Operating Procedure
SRC	Scientific Review Committee
T. bili	Total bilirubin
TBI	Total body irradiation
TRM	Transplant-related mortality
TTP	Time to progression
UCB	Umbilical Cord Blood
ULN	Upper limit of normal
UNK	Unknown
URD	Unrelated donor

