Serious Adverse Event (SAE): Any adverse event occurring that results in any of the following outcomes: death, a life threatening adverse event, a persistent or significant disability/incapacity, a congenital anomaly, requires intervention to prevent permanent impairment or damage. Unless the Principal Investigator is using an investigational agent, s/he is not bound by the definition in Title 22 CFR. Stanford IRB definition(s) and requirements apply when applicable, Unanticipated Problems Involving Risks to Participants or Others (UPs) and Unanticipated Adverse Device Effect (UAD)

All grades 3-5 organ-related adverse events not due to the primary malignancy or pre-existing condition will be collected from day 0 through resolution of the SAE. Grade 4 infusion reactions will be reported expeditiously and as a separate listing in the FDA Annual Report.

Distinction between Serious and Severe Adverse Events: The term severe is used to describe the intensity (severity) of a specific event, for example mild, moderate or severe. The event itself however, may be of relatively minor medical significance, for example a severe headache. This is not the same as serious, which is based on the patient/event outcome and is usually associated with events that pose a threat to the patient's life or functioning. Seriousness, not severity, serves as a guide for defining regulatory obligations.

All Adverse events will be graded using the NCI Common Terminology Criteria for Adverse Events (CTCAE) version 4.3 found on the following website:

http://ctep.cancer.gov/reporting/ctc.html

The Principal Investigator (PI) or designee will assess each Adverse Event (AE) to determine whether it is expected or unexpected according to the Informed Consent, Protocol Document, or Investigator's Brochure; and its

relationship to the investigational product.

For the purpose of this study, only AE's found to be directly related to a study-mandated intervention will be captured. The following adverse events, if felt to be related to study treatment, will be captured, but not reported as SAEs:

- Hospitalization, prolongation of hospitalization, or escalation of care due to study-mandated intervention
- Disease Relapse
- Any problems with CliniMACS device during cell separation or inability to achieve CD34+ cell and CD3+ cell target doses
- Any positive culture of HSCT product
- Failure to engraft or graft rejection

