All Serious Adverse Events (SAEs) will be tracked until resolution. SAEs will be collected from the time of stem cell infusion until 30 days post cell infusion. SAEs will be reported to the IRB if they meet the definition of expedited reporting per institutional regulations. All AE's and SAE will be reported at continuing renewal.

Reports (copy of faxed MedWatch) will also be sent to Miltenyi Biotec Incorporated, to the director of Regulatory Affairs and Safety Officer at [contact].

Serious Adverse events will be reported on the MedWatch form 3500a when it meets the definition of expedited FDA reporting. All deaths will be examined to determine if they are related to the use of the CliniMACS device or infusion of manipulated product. If the death is determined to be related, the event leading to the death must be reported within 24 hours of the Investigator's awareness of the event.

The following SAEs require expedited reporting (as soon as possible but within at least 7 calendar days of the investigator learning of the event):

Deaths: All deaths up to 100 days post-transplant. This includes deaths from the common and expected grade 3-4 toxicities noted below. Deaths that occur outside of Stanford will be reported within 5 working days of knowledge of the death. It must be noted that obtaining detailed information on the cause and circumstances of a death occurring at another institution can be difficult. Excludes deaths related to relapse of underlying disease, which will reported in the annual report.

All serious and unexpected toxicities defined as those toxicities not identified in the transplant literature or in the consent form and that are felt to be related to protocol-mandated procedures.

The following will not be reported as SAEs:

- Hospitalizations: Approximately 50% of allogeneic transplant recipients will be readmitted to the hospital. The
 most common indications for readmission of an allogeneic HCT recipient are fever, failure to maintain nutritional
 status and graft versus host disease. Only hospitalizations felt to be related to study mandated interventions
 should be reported as SAE's.

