10 MEASUREMENT

10.1 Primary and Secondary Outcome measures

The primary outcome will be severe (grade III/IV) acute graft-versus-host disease.

Secondary outcomes will be engraftment date (ANC>500 for 3 consecutive days, and >80% donor cells in blood), graft failure and graft rejection, immune recovery, infection, CMV infection and disease, EBV-related PTLD transplant-related toxicity and mortality, transplant-related mortality, grade 3/4 stem cell product infusion-related toxicity, relapse, DFS, OS.

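### As worded, the infusion-toxicity outcome leaves out a fatal infusion reaction, and the synopsis reporting sentence conflicts with section 8.2 on grade 5 events and on an undefined TRM exemption

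*Combined protocol and SAP*

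**What the plan says.** **Infusion toxicity.** Under severe toxicities, the synopsis list of secondary endpoints states: "This will include grade 3/4 stem cell product infusion-related toxicity". Section 10.1 repeats the grade range in its list of secondary outcomes: "grade 3/4 stem cell product infusion-related toxicity, relapse, DFS, OS". Section 8.2 adds a rule for expedited reporting and a separate annual listing of infusion reactions, and the only grade it names there is 4.

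**Synopsis reporting sentence.** The safety text under the discontinuation criteria limits what the principal investigator evaluates and reports to grades 3 and 4, and within those grades to "adverse reactions that are unexpected and possibly related to the investigation in process and are not expected TRM as per protocol definition".

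**Section 8.2.** The adverse event section goes further: "All grades 3-5 organ-related adverse events not due to the primary malignancy or pre-existing condition will be collected", from day 0. Its expedited category covers "All deaths up to 100 days post-transplant. This includes deaths from the common and expected grade 3-4 toxicities noted below". Deaths related to relapse are taken out of that category and go to the annual report. The section also requires every death to be examined for a relation to the device or the infused product. Its exemption for common and expected toxicities applies only to grade 3-4 events that are not fatal.

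**The concern.** An outcome that describes harm from an infused product should count the worst form of that harm. If the grade range ends at 4, the most serious possible event drops out of the numerator and the tabulated rate looks better than it is.

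The synopsis sentence raises a different problem. It stops at grade 4, yet it carves out a category of mortality, and it relies on a definition that the text supplied does not contain. In section 8.2 a fatal outcome ends the exemption for expected toxicity. In the synopsis, being expected TRM creates an exemption. Someone working from the synopsis and someone working from section 8.2 would follow different reporting rules, and the synopsis sentence sits directly before the reference to the stopping rules.

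**Working it through.** The plan gives no figure of its own to reproduce here. The check is a comparison of texts, followed by a small calculation of the effect on the tabulation.

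**1. Grade range, place by place.** Section 8.2 adopts the CTCAE scale. I take grade 5 to mean a fatal event.

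| Place | Subject | Grades named |
|---|---|---|
| Synopsis, Secondary Endpoint(s) | Infusion toxicity | 3/4 |
| Section 10.1 | Infusion toxicity | 3/4 |
| Section 8.2 | Infusion reactions, separate listing | 4 |
| Synopsis, Discontinuation Criteria | Reactions evaluated and reported | 3 or 4 |
| Section 8.2 | Organ-related adverse events | 3-5 |
| Synopsis and section 10.2, toxicity stopping rule | Acute GvHD, infection, unexpected toxicity, to 4 weeks | IV and above |

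None of the three places that name infusion toxicity reaches grade 5. The general collection rule in section 8.2 does, and so does the stopping rule.

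**2. Search for a TRM definition.** The abbreviation list expands TRM as "Transplant-related mortality" and adds no criteria. The synopsis gives time points for it as an endpoint (Day 100 and one year). Sections 1.2, 2.4 and 10.1 list it as an outcome. The nearest text is the section 8.2 list of common and expected toxicities, but that list is restricted to non-fatal events, so it cannot define an expected mortality. Some pages were not supplied, section 6.3 among them, and Appendix B shows only its heading. Agent ordering and graft-failure criteria are unlikely places for a TRM definition, but the supportable statement is that there is none in the text supplied.

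**3. Internal logic of the synopsis sentence.** The event must be grade 3 or 4, unexpected, possibly related and not expected TRM. The first condition already excludes fatal events, and the second already excludes expected ones. The TRM clause therefore removes almost nothing more. It mainly signals that expected deaths need not be reported, which section 8.2 contradicts.

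**4. Effect on the infusion-toxicity tabulation.** Inputs: n = 30 (the sample size in the synopsis and section 12). Assumptions: one fatal infusion reaction, no grade 3 or 4 reaction, and the event recorded at its highest grade. The intervals are exact (Clopper-Pearson) 95% limits.

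- Literal reading, 0 events: the upper limit is 1 − 0.025^(1/30) = 0.116, so 0/30 with 95% CI 0 to 11.6%.
- Grade 5 counted, 1 event: 1/30 = 3.3%. The lower limit is 1 − 0.975^(1/30) = 0.0008, or 0.1%. The upper limit solves (1−p)^30 + 30p(1−p)^29 = 0.025, which gives p = 0.172, or 17.2%.

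**5. Where the same death would still appear.** It would appear in the examination of all deaths under section 8.2, in expedited reporting if it occurred by day 100 and was not relapse-related, in overall survival, and in TRM if judged transplant-related. If it was an unexpected toxicity within 4 weeks, it would also trigger the halt in section 10.2.

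**The case against.** The strongest reply is that the protocol as a whole does not lose fatal events. Section 8.2 has all deaths examined for a relation to device or product, whether expected or not. The toxicity stopping rule stands in the same synopsis row, has no upper grade limit and carries no TRM exemption. Section 4.3 lets the investigator end the study for significant graft-related toxicity at any grade. TRM and overall survival are endpoints. The synopsis wording also only includes grade 3/4 infusion toxicity within severe toxicities, which does not cap that wider outcome. Fatal infusion reactions should be rare: the background section reports no significant infusion-related toxicities in the earlier multicentre trial.

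Most of this stands, and it limits the point to one tabulation and one reporting sentence. It does not remove either. The infusion item is named separately in section 10.1 with its own grade range, and that range omits death. The stopping rule is a partial backstop: it ends at 4 weeks and, apart from GvHD and infection, covers only unexpected toxicity.

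A reader might go further and infer that the synopsis exempts a countable number of deaths. The background cites 11% day-100 mortality and 37% TRM, and applied to 30 recipients these give 30 × 0.11 = 3.3 and 30 × 0.37 = 11.1. The documents do not support that inference. The synopsis sentence already covers only unexpected, possibly related, non-fatal grades, so those deaths were never within it for the TRM clause to remove. In addition, the 37% has no stated time point and was mostly due to infection, and the same background gives lower TRM figures (19% at one year, under 20% at two years).

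**Conclusion.** The point holds at minor severity. Followed literally, the infusion-toxicity outcome does not count a fatal infusion reaction. One such case would read 0/30 (95% CI 0 to 11.6%) instead of 1/30 (3.3%, 0.1 to 17.2%), under the assumptions stated with that calculation. The synopsis reporting sentence conflicts with section 8.2 on the upper grade and on deaths from expected causes, and its TRM exemption has no definition behind it in the text supplied.

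Two stronger readings should be resisted. The documents do not let deaths go unevaluated, because section 8.2 examines all of them. Nor does section 8.2 expedite every early death: relapse-related deaths are excluded, so the contrast is with deaths to day 100 other than those.

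**What to change.** - In the synopsis endpoint list and in section 10.1, count infusion-related toxicity as grade 3-5 (or grade 3 and above).
- In section 8.2, extend the infusion-reaction sentence so that its separate listing also covers grade 5.
- In the synopsis reporting sentence, cover grade 5, delete the exemption for expected TRM, and refer to section 8.2 for deaths.

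Deleting the exemption does not define TRM, which remains a secondary endpoint at Day 100 and one year. A one-sentence definition could be added in the same amendment.

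The cost is wording only. Section 8.2 already has every death examined for a relation to the device or product, and sample size and stopping boundaries do not change. The reported infusion-toxicity figure could be slightly less favourable.

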The stopping rule for graft failure yields the probability of stopping the trial of 0.05 if the rate of graft failure is 0.1. The probability of stopping the trial is 0.41 if the graft failure rate is 0.2, 0.82 if the graft failure rate is 0.3, and 0.96 if the graft failure rate is 0.4. These probabilities were calculated based on the binomial distribution.

If the study reaches a stopping boundary, the study will be suspended. Proper use of the stopping rule table will be ensured by the Study Investigator.

Stopping rule for Grade \geq IV toxicity: If any patient develops grade \geq IV acute GvHD, grade \geq IV infection, or any unexpected grade \geq IV toxicity by 4 weeks post-transplant, the protocol will be halted and the processing re-evaluated before

	proceeding.
	Conditions for individual patient termination: Disease progression Need for exclusionary concurrent treatment (per PI discretion) Withdrawal of informed consent Protocol non-compliance
	The PI, through the reports from the Stem Cell Laboratory, will also monitor system performance based on: Cellular composition of final product Yield (% recovery) of CD34+ cells from the starting product CD3+ cell reduction Sterility Purity
Sample Size	The study will enroll 30 transplant recipients at Stanford.
Statistical Methodology	Statistical analysis results will be reported using summary tables, figures, and data listings. Continuous variables will be summarized using the mean, standard deviation, median, minimum, and maximum. Categorical variables will be summarized by numbers and percentages of subjects in corresponding categories. All raw data obtained from the case report form (CRF) and any derived data will be summarized and included in data listings. Missing data will not be imputed.

List of Abbreviations and Definition of Terms

List of Abbreviations	List of Appreviations and Definition of Terms
AE	Adverse event
AdV	Adenovirus
aGvHD	Acute Graft-versus-Host Disease
ALL	Acute Lymphoblastic Leukemia
Allo	Allogeneic
AML	Acute Myelogenous Leukemia
ANC	Absolute Neutrophil Count
ВМ	Bone marrow
BM bx.	Bone marrow biopsy
ВМІ	Body mass index
BMT	Bone Marrow Transplant
BP	Blood pressure
BSA	Body surface area
°С	Degrees Celsius
СВ	Cord blood
CBC	Complete blood count
CD	Cluster of Differentiation
CFR	Code of Federal Regulations
cGvHD	Chronic Graft-versus-Host Disease
CIBMTR	Center for International Blood and Marrow Transplant Research
CML	Chronic Myelogenous Leukemia
CMV	Cytomegalovirus

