It has been well established that allogeneic peripheral blood stem cells (PBSC) recruited into the blood by administering G-CSF can successfully and durably engraft in both matched (13,14) or mismatched (15,16) transplant settings. PBSC recruited with cytokines generally engraft earlier and contain a larger number of HSC compared to marrow HSC (14,15).

Much of the work that has been done with this approach has been reported by a group in Perugia, Italy. They used the CliniMACS® device to lower the T cell content of the donor PBSC to a median of 1 x 10^4 /kg (range 0.04 – 3 x 10^4 /kg). Ninety-one percent of patients had primary engraftment. Six of seven patients who did not have primary engraftment were successfully engrafted after a second transplant, making the overall engraftment rate 99%. Grade III-IV acute GvHD occurred in 2% of patients. The transplant-related mortality was 37%, with the majority of deaths due to infection (bacterial, viral, and fungal). Relapse occurred in 16% of 66 patients who were in remission at the time of transplant. The two-year EFS for patients in remission was 48% for AML and 46% for ALL (17).

The results of haplocompatible transplantation in children have been encouraging. Handgretinger reported a 46%

two years EFS in patients with ALL in CR1-3 (18) Ortin et al. reported 75% EFS of patients with ALL in CR2/3 with median follow-up of 18 months (range 6-29) (19). The international experience was reviewed at a conference in Naples in 2004. Lang updated the Tubingen, Germany experience when he reported a 44% 2 years EFS for 21 children with ALL in CR1-3 (20)

Advantages of haplocompatible transplantation are rapid engraftment and the very low incidence of severe acute GVHD. Ortin et al. reported a median time to ANC > 500 and to platelet count > 50,000 of 12 and 20 days, respectively, with the incidence of grade III/IV acute GvHD being 5% (19). Lang reported a 1% incidence of grade III/IV acute GvHD (21).

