In a retrospective review of the experience of 3 investigators in the U.S. (Cowan, Gilman, Sleight) with alternative (haplocompatible) donor transplant using CD34+ cell selection for T cell depletion, 13/18 (72%) were surviving with follow-up of 7 months – 7 years (median 31 months)(22). The median patient age was 8 years (range 1-20). Patient with malignancy (n=13) included: AML - CR1 (primaryinduction failure, failed cord blood transplant) [1], CR2 [3]; MDS - RA/RARS [2], RAEB [2]AM (and Fanconi anemia, FA) [1]; CML - CP2 [1]; ALL - CR3 [2]; NHL - CR2 [1]. Patients with non-malignant (n=5) disease included severe aplastic anemia (1 with prior bone marrow transplant three years earlier) [4] and Wiskott-Aldrich syndrome [1].

Fourteen donors were a 3/6 HLA match and 5 were a 4/6 match (one patient had two transplants using different donors). A CD34-positive selection device – Miltenyi CliniMACS $^{\otimes}$ (15), Isolex (3) – was used to select stem cells and deplete T lymphocytes. Patients received a median of 18 x 10 6 CD34+ (stem) cells/kg (range 6-28) and 3 x 10 4 CD3+ (T) cells/kg (range 0.3-11).

Sustained primary engraftment occurred in 15/18 (83%) patients. Primary graft failure occurred in one patient. Two patients had immunological rejection following HHV-6 reactivation. They both engrafted after a second transplant; therefore the overall engraftment rate was 94%. The median time to an ANC >0.5 x 10⁹/L was 12 days (range 9-21). Platelet recovery occurred in 16/18 at a median of 17 days (range 9-22). Grade II acute GvHD was seen in 4/17 patients (24%). Grade III-IV acute GvHD was seen in 1 pt. (6%) with overlap syndrome (acute + chronic GvHD) associated with HHV-6 reactivation. Nine patients received DLI and/or stem cell boosts (boosts for graft rejection); 4 had grade II GvHD (3/4 had a history of acute GvHD) and none had grade III-IV GvHD. After DLI and/or stem cell boost, two patients developed extensive chronic GvHD and one developed overlap syndrome. The day 100 mortality and one year transplant-related mortality were 11% and 19%, respectively. Four patients (of 13 at risk, 31%) have relapsed; 1 patient with cytogenetic relapse is in CR > 1 year later. The 2 year predicted survival is 64% (60% for 13 patients with malignant disease and 75% for 5 patients with non- malignant disease).

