10.2 Stopping Rules

The study includes stopping rules based on the incidence of graft failure (or graft rejection), and acute GVHD.

Stopping rule for primary graft failure: The first 30 enrolled patients (related and unrelated) will be evaluated for the stopping rule for primary graft failure. The trial is stopped if there are \geq b graft failures out of k resolved patients. Only points where stopping is possible are listed.

k	2	4	5	6	8	9	10	12	13	14	15	16	18	19	20	21	23	24	25	26	27	28	30
b	2	3	3	3	4	4	4	5	5	5	5	5	6	6	6	6	7	7	7	7	7	7	8

The stopping rule for graft failure yields the probability of stopping the trial of 0.05 if the rate of graft failure is 0.1. The probability of stopping the trial is 0.41 if the graft failure rate is 0.2, 0.82 if the graft failure rate is 0.3, and 0.96 if the graft failure rate is 0.4.

These probabilities were calculated based on the binomial distribution. The stopping rule was generated as described by Ivanova et al. (40).

If the study reaches a stopping boundary, the study will be suspended. At this point it may be terminated by the PI or submitted to the safety monitor with a description of the failures to date and a rationale for why the study should be continued. Proper use of the stopping rule table will be ensured by the Study Investigator.

Stopping rule for Grade \geq IV toxicity: If any patient develops grade \geq IV acute GvHD, grade \geq IV infection, or any unexpected grade \geq IV toxicity by 4 weeks post-transplant, the protocol will be halted and the processing reevaluated before proceeding.

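### No stopping boundary covers transplant-related mortality: from week 4 to Day +100 it is left to unquantified investigator discretion and death reporting, although the synopsis refers unacceptable toxicity to the stopping rules

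*Combined protocol and SAP*

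**What the plan says.** The synopsis (Discontinuation Criteria) states that if the treatment is clearly inferior to other options "or the toxicity is unacceptable we will follow the stopping rules". Section 10.2 gives their scope: "The study includes stopping rules based on the incidence of graft failure (or graft rejection), and acute GVHD".

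The two rules, set out in both the synopsis and Section 10.2, are:

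- **Graft failure.** "The trial is stopped if there are ≥ b graft failures out of k resolved patients", with a table running from k = 2 to k = 30. Crossing it suspends the study. The investigator may then terminate, or make a case to the safety monitor for continuing.
- **Grade IV or higher events.** Any acute GvHD, infection or unexpected toxicity of that grade halts the protocol while processing is re-evaluated. A 4-week limit stands at the end of the list of triggers.

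Mortality appears elsewhere without a threshold. The synopsis makes TRM a secondary endpoint at Day 100 and one year. Section 12 provides annual descriptive interim analyses. Section 8.2 requires expedited reports, within 7 calendar days, for "Deaths: All deaths up to 100 days post-transplant", excluding relapse deaths, and has every death examined for a link to the device or product. Section 4.3 lets the investigator terminate the study for significant toxicity related to the graft, or for inferior effectiveness.

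**The concern.** The synopsis points to rules that do not contain the response it implies. The protocol's own background gives reason to watch mortality. Section 2.1 cites one series with TRM of 37%, mostly from infection, and another in which only 3 of 17 patients exceeded 100 CD4 cells by day 100. It concludes that immune recovery was slow and that infections contributed to deaths. A toxicity window that closes at week 4 covers only the first part of that risk period.

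Graft failure has a numeric boundary with stated operating characteristics, while death from the transplant has none. If deaths accumulate between week 4 and Day +100, nothing in the plan fixes in advance how many should prompt a pause. The judgment would be made case by case, after the data are seen, by the person running the study.

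**Working it through.** **1. Coverage of the rules**

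| Event | Graft-failure rule | Grade IV rule | Other provision |
|---|---|---|---|
| Death by week 4 from grade IV GvHD, infection or unexpected toxicity | only if also a primary graft failure | yes, one event halts | 8.2, 4.3 |
| Non-relapse death, week 4 to Day +100 | only if also a primary graft failure | not if the 4-week limit governs all triggers | 8.2, 4.3 |
| Accumulating count of deaths | no | no | descriptive only (Section 12) |

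**2. Reproducing the plan's own figures**

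Inputs: the 23 (k, b) pairs in Section 10.2 and 30 patients. Let f_n(x) be the probability of not having stopped, with x events, after n patients:

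f_n(x) = (1 − p) f_{n−1}(x) + p f_{n−1}(x − 1)

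At each listed n, the mass with x ≥ b is moved to stopped. For example, at k = 2, b = 2 the stopping probability is p²: 0.01 at p = 0.1 and 0.04 at p = 0.2.

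| True rate | Stated | Recomputed |
|---|---|---|
| 0.1 | 0.05 | 0.049 |
| 0.2 | 0.41 | 0.408 |
| 0.3 | 0.82 | 0.827 |
| 0.4 | 0.96 | 0.978 |

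The plan states: "The stopping rule for graft failure yields the probability of stopping the trial of 0.05 if the rate of graft failure is 0.1" and "The probability of stopping the trial is 0.41 if the graft failure rate is 0.2". Both reproduce. The last row differs by 1.8 points, which does not matter here.

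**3. The same table applied to non-relapse deaths by Day +100 (illustration only)**

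Recipients are counted in enrolment order, each once Day +100 status is known. The expected number of deaths is 30 × rate.

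| True rate | Expected deaths in 30 | P(suspend) | Expected patients counted |
|---|---|---|---|
| 10% | 3.0 | 0.049 | 29.1 |
| 11% | 3.3 | 0.067 | 28.8 |
| 20% | 6.0 | 0.408 | 23.7 |
| 30% | 9.0 | 0.827 | 15.6 |
| 37% | 11.1 | 0.955 | 11.2 |

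The 11% row is the Day 100 figure from Section 2.1: "The day 100 mortality and one year transplant-related mortality were 11% and 19%, respectively". It is a rough anchor. It is all-cause mortality in 18 patients, about 2 deaths (2/18 = 11.1%), with an exact 95% interval of 1.4% to 35%. The 37% has no time point in the text, so that row is not a Day +100 benchmark.

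**4. What the early halt already catches**

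Suppose a share s of Day +100 TRM consists of grade IV rule events by week 4. The documents do not give s. The chance of at least one halt in 30 patients is 1 − (1 − TRM × s)^30.

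| TRM | s = 0 | s = 10% | s = 25% | s = 50% |
|---|---|---|---|---|
| 20% | 0 | 0.46 | 0.79 | 0.96 |
| 30% | 0 | 0.60 | 0.90 | 0.99 |

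For TRM 30% and s = 10%: 1 − 0.97^30 = 0.60.

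**5. Why the counting order matters**

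If a death counts when it occurs but a survivor only at Day +100, deaths enter the count early and inflate the ratio. A simulation of 30 patients, assuming random accrual and deaths uniform over days 0 to 100, gives these false-suspension probabilities:

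| Patients per year | True 10% | True 11% |
|---|---|---|
| 5 | 0.06 | 0.08 |
| 10 | 0.07 | 0.10 |
| 15 | 0.09 | 0.12 |
| 30 | 0.15 | 0.18 |

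Counted in enrolment order, they are 0.05 and 0.07.

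**The case against.** A reader might infer that the trial would run on at any Day +100 mortality, or that a true rate of 30% would cross no boundary. The documents do not support either inference.

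- Section 4.3 lets the investigator stop for significant graft-related toxicity with no time limit, and Section 8.2 puts non-relapse deaths to Day 100 before the investigator promptly.
- Day +100 mortality includes early deaths, and one grade IV infection or GvHD by week 4 halts the protocol, whether or not it is fatal.
- The graft-failure rule has no 4-week limit, so a later death that is also a primary graft failure counts.

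The 4-week limit is also ambiguous. It may attach only to the last item, unexpected toxicity. A grade IV infection or GvHD would then halt the protocol at any time, and the gap would be much smaller.

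Nor do the documents show that most of these deaths fall after week 4. The 37% is undated. The two infection deaths dated in Section 2.1 came at 7 and 23 months, which a Day +100 boundary would also miss. The 47-patient multicentre trial reported TRM below 20% at 2 years. Finally, the synopsis sentence follows one that sets expected TRM apart from reportable reactions, so it may never have been meant as a promise about mortality.

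All of this limits the claim. What remains is that the safeguards after week 4 carry no number, and that the early halt responds to a single event rather than to accumulated deaths.

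**Conclusion.** The point holds as a gap in the stopping rules. No boundary has mortality as its event. If the 4-week limit governs all three triggers, which is the natural reading, TRM from week 4 to Day +100 is left to discretion and reporting. A boundary driven by mortality therefore has probability 0 of acting at every rate, because none exists. The existing table would act with probability 0.41 at 20% and 0.83 at 30%.

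Those probabilities assume independent patients with a common rate, enrolment-order counting and a table designed around a 10% graft-failure rate. They show what is attainable with 30 patients and do not establish 10% as an acceptable mortality. The stated graft-failure probabilities are not in question. This should be changed, but it does not invalidate the design.

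**What to change.** Reconcile the synopsis with Section 10.2 in two places.

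1. State whether the 4-week limit applies to all three grade IV triggers or only to unexpected toxicity. The clinical team decides which.
2. Add a boundary along these lines: *Non-relapse deaths by Day +100 are monitored with a boundary generated by the method used for graft failure, at an acceptable rate set by the clinical team. Recipients are counted in enrolment order, each once Day +100 status is known. Crossing the boundary suspends the study for review.* Give its operating characteristics as for graft failure, and say how recipients who relapse or leave the study before Day +100 are counted.

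Using non-relapse deaths matches what Section 8.2 already reports, so no new data are needed. If the existing table were kept, the chance of a needless suspension would be about 5-7% at a true rate of 10-11%. A suspension is recoverable, since Section 10.2 allows a case for continuing. Enrolment-order counting has a price: a death cannot be counted until every earlier recipient's status is known, so the boundary reacts more slowly. If the team prefers to count deaths as they occur, the boundary should be recalibrated, because the existing table would then suspend needlessly in about 6-18% of trials under the accrual and timing assumptions above.
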